#### **9.7.2.1 Abnormal Laboratory Results**

For each quantitative hematology, chemistry, endocrinology, and reproductive endocrinology (AMH test only) laboratory parameter, observed values will be compared to normal laboratory reference ranges and classified as “Low”(where applicable), “Normal”, “High (if applicable). For each laboratory parameter, a 4x4 contingency table (shift table) will be displayed that summarizes the counts of subjects who were classified as “Low”, “Normal”, “High” or result missing at Baseline vs. “Low”, “Normal”, “High” or result missing at Post-baseline time points, where Post-baseline time points are Day 28, Day 56, Day 85/ETD, and Day 113. Separate shift tables will be generated for each treatment group at each visit. A listing of abnormal laboratory results will be provided.

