3. FEV1/FVC $< 60\%$
4. Body mass index (BMI) < 18 kg/m² or ≥ 40 kg/m² at Screening
5. History of upper or lower respiratory tract infection or recent significant change in pulmonary status within 4 weeks of the Baseline Visit (Day 0)
6. History of cystic fibrosis
7. History of opioid use within 1 week of the Baseline Visit (Day 0)
8. Requiring concomitant therapy with prohibited medications (see [Section 5.7](#))
9. Treatment with biologic therapies within 8 weeks or 5 half-lives prior to the Baseline Visit (Day 0), whichever is longer
10. Treatment with strong CYP3A4 inhibitors within 4 weeks prior to the Baseline Visit (Day 0) (see [Appendix B](#))
11. Treatment with any investigational therapy within 4 weeks (investigational biologic therapies within 8 weeks) prior to the Baseline Visit (Day 0)

12. Serum creatinine, total bilirubin, alanine aminotransferase (ALT) or aspartate aminotransferase (AST) > 2x the upper limit of normal (ULN) during screening
13. Positive test for any drug of abuse
14. History of malignancy within 5 years prior to the Baseline Visit (Day 0), with the exception of completely treated and non-metastatic basal cell carcinoma or squamous cell carcinoma of the skin
15. Any known psychiatric diagnosis meeting DSM-5 criteria which may confound the assessment of serlopitant safety or efficacy, or interfere with the subject's ability to comply with protocol-mandated activities, within 3 years prior to randomization. Examples of such DSM-5 diagnoses include but are not limited to major depressive disorder, bipolar disorder, schizophrenia, psychotic disorder, intellectual disability, severe alcohol use disorder
16. Known active hepatitis infection
17. Known history of human immunodeficiency virus (HIV) infection
18. History of hypersensitivity to serlopitant or any of its components
19. Currently pregnant or breastfeeding female subject
20. Females of childbearing potential who are unable or unwilling to practice highly effective contraception (pregnancy prevention)
21. Presence of any medical condition or disability that, in the investigator's opinion, could interfere with the assessment of safety or efficacy in this trial or compromise the safety of the subject, including clinically significant ECG abnormalities during screening

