6.2.3 Clinical Laboratory Assessments

Samples for hematology, chemistry, urinalysis, and serum pregnancy testing (when necessary) will be collected as outlined in [Appendix A](#) and at unscheduled study visits when clinically indicated, and analyzed at a central laboratory unless otherwise specified. Detailed instructions regarding sample collection, preparation, and shipment can be found in the laboratory manual. Laboratory assessments will include the following:

- Hematology: hematocrit, hemoglobin, red blood cell count, red blood cell indices, platelets, white blood cell count, white blood cell differential (neutrophils, lymphocytes, monocytes, basophils, eosinophils)
- Chemistry: sodium, potassium, chloride, bicarbonate, glucose, blood urea nitrogen, creatinine, calcium, phosphorus, magnesium, albumin, ALT, AST, alkaline phosphatase, total bilirubin, LDH, uric acid, total protein, lipid panel
- Pregnancy testing: all females of childbearing potential will have a local urine pregnancy test performed. Positive or equivocal urine pregnancy test results will be confirmed by a serum pregnancy test analyzed at a central laboratory. A serum pregnancy test will be done at Screening.
- Urinalysis: color, clarity, pH, specific gravity, bilirubin, glucose, ketones, leukocytes, nitrite, blood, protein, urobilinogen, microscopic analysis
- Endocrine: TSH, free T4, cortisol, corticotropin
- Reproductive endocrinology (for all female subjects under 55 years of age at consent): serum FSH, LH, estradiol, progesterone, Anti-Mullerian hormone (AMH)

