The study is designed to evaluate the efficacy profile of serlopitant 5 mg versus placebo. The sequential testing procedure will be employed to control the overall Type I error rate at 5% with respect to multiple comparisons for the primary and key secondary endpoints. The procedure will be done in a hierarchical manner. The order of the testing is outlined below.

1. Primary endpoint: serlopitant 5 mg versus placebo
2. Key secondary endpoint #1: serlopitant 5 mg versus placebo
3. Key secondary endpoint #2: serlopitant 5 mg versus placebo
4. Key secondary endpoint #3: serlopitant 5 mg versus placebo
5. Key secondary endpoint #4: serlopitant 5 mg versus placebo

First, the test ranked as first will be tested and the difference will be declared statistically significant if the one-sided p value is less than 0.05. Second, in case that the difference for the first comparison is statistically significant, the comparison ranked as second will be tested, and the difference will be declared statistically significant if the one-sided p-value is less than 0.05. The testing will continue as long as the previously ranked objective was statistically significant.

All other efficacy variables will be tested at the 0.05 level of significance without multiplicity adjustment.

8.10 **Safety Analyses**

8.10.1 *Adverse Events*

The incidence of all AEs and treatment-related AEs will be tabulated by treatment received. These AEs will be classified by system organ class and preferred term using the Medical Dictionary for Regulatory Activities (MedDRA). For incidence reporting, if a subject reported more than one AE that was coded to the same system organ class or preferred term, the subject will be counted only once for that specific system organ class or preferred term. An overview of AEs, which includes subject incidence of AEs, treatment-related AEs, AEs by severity, SAEs, deaths, and AEs leading to discontinuation, will be presented.

SAEs will be listed and summarized in a similar manner to AEs.

8.10.2 *Clinical Safety Laboratory Results*

Clinical safety laboratory values will be measured by a central laboratory. Summary statistics for actual values and for changes from baseline will be tabulated for laboratory results by scheduled visit. Graphs of laboratory values over time will also be produced.

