Subjects with clinical laboratory values outside of the normal reference range at any post-baseline assessment will be summarized. Shifts from baseline laboratory values will be tabulated.

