8.10.4 Electrocardiograms

The overall ECG assessment (abnormal or normal) will be summarized along with a summary of how many subjects developed a post treatment abnormal result. The study relevance of the finding will be provided in a listing.

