**Table 2: Analysis Windows**

Analysis Visit	Range	Target Day
Baseline	Day $\leq$ 1	Day 1
Day 28 (Week 4)	Day 2 to Day 42	Day 28
Day 56 (Week 8)	Day 43 to Day 70	Day 56
Day 84 (Week 12)	Day 71 to min (Day 91, TRTEDT+7)	Day 84
Day 112 (Follow-Up)	> min (Day 91, TRTEDT+7)	Day 112

+TRTEDT – date of last study medication

The Follow-Up assessment will be the last assessment available that is at least seven days after the end of treatment. Should no post treatment assessments be available the subject will not have a follow-up assessment. Any assessments reported after the date of last study medication will be considered as a follow-up assessment.

For other efficacy and safety endpoints, the study visits as specified in the protocol will be utilized as analysis visits.

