### 9.7.5 12-Lead Electrocardiograms

Electrocardiograms (12-lead) will be obtained at Screening, Day 28, Day 56, Day 85/ETD, and Follow-Up (Day 113). The observed results and change from baseline will be summarized descriptively by visit and by treatment group. ECG variables include heart rate, PR, QT, QTc, RR intervals and QRS duration. QTcB and QTcF are also calculated. Baseline for laboratory tests is defined as the last assessment performed prior to Day 1 dosing date.

The overall ECG assessment will be summarized by visit and by treatment. The count and percentage of subjects with QTcF > 450, 480 and 500 msec and a change from baseline value > 30 and 60 msec will be summarized by visit and by treatment group.

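### The SAP tabulates laboratory and ECG abnormalities by visit only, so the protocol's per-subject counts are not delivered and unscheduled results have no stated rule

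*SAP*

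**What the plan says.** **Protocol.** Section 8.10.2 specifies three laboratory outputs. The first is descriptive: "Summary statistics for actual values and for changes from baseline will be tabulated for laboratory results by scheduled visit". The second is per subject: "Subjects with clinical laboratory values outside of the normal reference range at any post-baseline assessment will be summarized". The third is a tabulation of shifts from baseline. The synopsis repeats all three. For ECG, section 8.10.4 asks for the overall assessment together with a "summary of how many subjects developed a post treatment abnormal result". Section 6.2.3 allows laboratory samples "at unscheduled study visits when clinically indicated", and sections 6.2.1 and 6.2.4 allow the same for vital signs and ECGs. Exclusion 12 in section 4.3 bars subjects with serum creatinine, total bilirubin, ALT or "aspartate aminotransferase (AST) > 2x the upper limit of normal (ULN) during screening", so values above the normal range but not above twice ULN are admissible.

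**SAP.** Section 7.3 sets windows for cough frequency and then states: "For other efficacy and safety endpoints, the study visits as specified in the protocol will be utilized as analysis visits". Section 9.7.2 lists all laboratory results and gives descriptive statistics, including change from baseline, by visit. Section 9.7.2.1 adds Low/Normal/High/missing shift tables for Day 28, 56, 85/ETD and 113 ("Separate shift tables will be generated for each treatment group at each visit") and a listing of abnormal results. Section 9.7.5 summarises the overall ECG assessment by visit. It counts subjects above three QTcF thresholds "and a change from baseline value > 30 and 60 msec will be summarized by visit and by treatment group". Section 9.7.4.1 counts potentially clinically important (PCI) vital signs at named scheduled visits.

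**The concern.** The protocol asks how many subjects in each arm were ever abnormal. The SAP answers how many were abnormal at each visit. These are different quantities, and the first is the usual basis for comparing arms on laboratory and ECG outliers.

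Two further gaps go with this. Results from unscheduled visits are taken because something prompted them, yet nothing says whether they enter any laboratory, ECG or vital-sign table. And with one High class, the shift table does not separate a subject who stays mildly raised from one who rises several-fold.

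The analytes are not arbitrary here. Protocol 1.3.1 reports mild liver weight increases in animals and, in rats, kidney tubule vacuolation and slight cardiac muscle degeneration, although at exposures above those anticipated in humans. SAP 8.1 classes analyses added after database lock as post hoc and exploratory, so the tables need to be specified beforehand.

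**Working it through.** The plan gives no figure on this point to reproduce. The check compares the texts and adds one illustration.

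**1. Laboratory commitments against SAP tables.**
- Descriptive statistics by scheduled visit (Protocol 8.10.2): delivered in SAP 9.7.2.
- Shifts from baseline (Protocol 8.10.2): delivered in SAP 9.7.2.1, per visit.
- Subjects out of range at any post-baseline assessment (Protocol 8.10.2): no SAP table. The nearest output is the listing of abnormal results.

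**2. Can the by-visit tables supply the any-time count?** Let p be the share out of range at each of four scheduled visits. The share out of range at least once is p if the same subjects are abnormal every time, 1 − (1 − p)^4 if visits are independent, and at most 4p if different subjects are abnormal each time. The documents give no p, so a range is assumed. The arm size is the planned 85.

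| p (assumed) | Same subjects each time | Independent visits | Different subjects each time |
|---|---|---|---|
| 1% | 1% (0.9 of 85) | 3.9% (3.3) | 4% (3.4) |
| 2% | 2% (1.7) | 7.8% (6.6) | 8% (6.8) |
| 5% | 5% (4.3) | 18.5% (15.8) | 20% (17.0) |
| 10% | 10% (8.5) | 34.4% (29.2) | 40% (34.0) |

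The same by-visit figures fit every entry in a row, so the per-subject count cannot be recovered from them, even before unscheduled samples are considered. Four visits apply to hematology and chemistry; endocrine tests are not drawn at Day 28 or 56 (Protocol Appendix A, note p).

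**3. Rise from a raised baseline.** Take a hypothetical subject with ALT at 1.8 × ULN, admissible under exclusion 12, who reaches 8 × ULN at a scheduled visit. The baseline class is High and the visit class is High. The subject falls in the same cell as one who stays at 1.8 × ULN. The change is 8 − 1.8 = 6.2 × ULN. SAP 8.1 includes minimum and maximum in descriptive statistics, so this rise could appear as that arm's maximum at that visit. That is one extreme per arm and visit, with no number of subjects and no link to baseline status.

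**4. ECG.** Protocol 8.10.4 asks for the number of subjects who developed an abnormal result. SAP 9.7.5 gives the overall assessment by visit, so the difficulty in step 2 recurs.

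**5. Unscheduled results.** SAP 7.3, 9.7.2, 9.7.2.1, 9.7.4.1 and 9.7.5 contain no rule for using unscheduled results and no worst-value rule. Such laboratory results reach the listings. Laboratory, ECG or vital-sign findings reach the adverse event tables only if the investigator judges them clinically significant (Protocol 7.1.3, SAP 9.7.1).

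**The case against.** The strongest reply is that the SAP already covers most of the ground, and several stronger readings that a reader might draw do not hold.

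- *That the shift tables are the only laboratory tables, so worsening from a high baseline is invisible.* Not supported: SAP 9.7.2 also tabulates observed values and change from baseline, and SAP 8.1 includes the maximum. What is missing is a count of subjects.
- *That the ECG tables miss worsening from a high baseline.* Not supported: SAP 9.7.5 counts QTcF changes above 30 and 60 msec, and the PCI criteria in SAP Table 3 also require a change from baseline.
- *That the protocol's any-assessment wording governs ECG and vital signs.* It covers laboratory values only. ECG has its own commitment in Protocol 8.10.4, and Protocol 8.10.3 asks for vital signs by measurement day.
- *That the SAP excludes unscheduled results.* It is silent. SAP 7.3 refers to protocol visits, and Protocol 6.5 itself provides for unscheduled visits.
- *That the loss can be sized by the share of short excursions falling between four-weekly draws.* This describes the sampling schedule. The documents give no excursion lengths, and an excursion that was never sampled cannot be recovered by any table.

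It is also fair that clinically significant findings are recorded as adverse events, graded by CTCAE v4.03 and tabulated by arm, and that by-visit laboratory statistics are what the protocol asks for. The protocol does not promise graded laboratory tables; that part of the remedy is an improvement.

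None of this supplies the two promised per-subject counts or a rule for unscheduled values. The adverse event route depends on individual investigator judgement.

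**Conclusion.** The point holds in this form. Followed as written, the SAP does not produce the protocol's summary of subjects with laboratory values out of range at any post-baseline assessment, nor its count of subjects who developed an abnormal ECG after treatment. No laboratory table counts subjects who worsen markedly from an already high baseline, and the handling of unscheduled results is left open.

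The practical size is not known. It depends on abnormality rates, their persistence across visits and the number of unscheduled samples, none of which the documents give. The figures above show only that by-visit tables leave the per-subject rate undetermined. The matter concerns safety reporting and does not touch the primary efficacy analysis. It should be corrected before database lock.

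**What to change.** Amend the SAP as follows.

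- **9.7.2.1:** Add, by arm, the number of subjects out of range at any post-baseline assessment for each parameter. Add a table of each subject's worst post-baseline value, including unscheduled and repeat results, against baseline. Use CTCAE v4.03 grade where one exists, and also multiples of ULN for ALT, AST and bilirubin. For parameters that can be abnormal in both directions, take the worst high and worst low separately.
- **9.7.5:** Add the number of subjects with any abnormal ECG after treatment, and apply the same worst-value rule, including unscheduled results, to the QTcF threshold and change counts.
- **9.7.4.1:** Apply that rule to the PCI counts.
- **7.3:** State that unscheduled results enter these worst-value tables, and whether they enter the by-visit tables.

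Keep all by-visit tables. The cost is SAP wording and a few extra tables from data already collected, with no added visits or samples.

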#### **9.7.3 Physical Examination**

Physical examination information will be listed.

### 9.7.4 Vital Signs

Vital signs will be collected at Screening, Baseline (Study Day -1), Day 1, Day 28, Day 56, Day 84, Day 85/ETD, and at Follow-Up (Day 113). Vital signs will be summarized by visit and by treatment group. Variables summarized include, systolic blood pressure (mmHg), diastolic blood pressure (mmHg), pulse rate (bpm), respiratory rate (per minute), and temperature. Baseline for laboratory tests is defined as the last assessment performed prior to Day 1 dosing date.

#### 9.7.4.1 Potentially Clinically Important (PCI) Findings in Vital Signs

At each post-baseline vital signs assessment, observed vital signs results will be categorized into the categories according to the following criteria (Table 3) of potentially clinically important (PCI) findings. The count and percentage of subjects with vital signs parameters at each category of potentially clinically importance (PCI) will be summarized by treatment group for Day 1, Day 28, Day 56, Day 84, Day 85/ETD, and Follow-Up (Day 113).

**Table 3: Potentially Clinically Important (PCI) Criteria for Vital Signs**

Parameter	Clinically significant value/change
Pulse rate	≤50 bpm and decrease from baseline ≥20 bpm ≥110 bpm and increase from baseline ≥20 bpm
Systolic BP	≤90 mmHg and decrease from baseline ≥20 mm Hg ≥160 mmHg and increase from baseline ≥20 mm Hg
Diastolic BP	≤50 mmHg and decrease from baseline ≥20 mm Hg ≥105 mmHg and increase from baseline ≥20 mm Hg
Respiration rate	≤8 breaths/min and ≤-30% change from baseline ≥25 breaths/min and ≥30% change from baseline

### 9.7.5 12-Lead Electrocardiograms

Electrocardiograms (12-lead) will be obtained at Screening, Day 28, Day 56, Day 85/ETD, and Follow-Up (Day 113). The observed results and change from baseline will be summarized descriptively by visit and by treatment group. ECG variables include heart rate, PR, QT, QTc, RR intervals and QRS duration. QTcB and QTcF are also calculated. Baseline for laboratory tests is defined as the last assessment performed prior to Day 1 dosing date.

The overall ECG assessment will be summarized by visit and by treatment. The count and percentage of subjects with QTcF > 450, 480 and 500 msec and a change from baseline value > 30 and 60 msec will be summarized by visit and by treatment group.

## 11.0 APPENDICES

### APPENDIX A: SAS SAMPLE CODES

A sample of the SAS code for MMRM analysis is provided as below:

```
/*GENERATE LOG-TRANSFORMED COUGH FREQUENCY FIRST*/

PROC MIXED DATA=LOGEFF METHOD=REML;
CLASS TRT01PN USUBJID AVISITN COUNTRY SEX;
MODEL LCHG = TRT01PN AVISITN COUNTRY SEX TRT01PN*AVISITN LBASE / DDFM=KR;
/*LCHG AND LBASE ARE BASED ON THE LOG-TRANSFORMED COUGH FREQUENCY*/
REPEATED / SUBJECT=USUBJID (TRT01PN) TYPE=UN;
LSMEANS TRT01PN*AVISITN / CL PDIFF;
  ESTIMATE 'TRT S - P ON DAY 28' TRT01PN -1 1
           TRT01PN*AVISITN -1 0 0 1 / CL LOWER LOWERTAILED;
  ESTIMATE 'TRT S - P ON DAY 56' TRT01PN -1 1
           TRT01PN*AVISITN 0 -1 0 0 1 / CL LOWER LOWERTAILED;
  ESTIMATE 'TRT S - P ON DAY 84' TRT01PN -1 1
           TRT01PN*AVISITN 0 0 -1 0 0 1 / CL LOWER LOWERTAILED;

RUN;
```

Where TRT01PN = planned treatment group in numeric (**1 = placebo, 2 = serlopitant 5 mg**); AVISITN = time point (i.e. Day 28, Day 56, and Day 84); COUNTRY (USA, UK); SEX (Female, Male); TRT01PN\*AVISITN = treatment by visit interaction; CHG = hourly cough frequency (on the log scale) - BASE (on the log scale); BASE = baseline hourly cough frequency (on the log scale); TYPE=UN specifies unstructured covariance matrix structure; METHOD=REML specifies the estimation method (REML is the default method); and DDFM=KR requests the Kenward-Roger method for the covariance matrix of the fixed-effect parameter estimates and denominator degrees of freedom for t and F tests.

A sample of the SAS code for ANOVA analysis of ranked 24-hour cough frequency at Week 12 (Day 84) is provided as below:

```
PROC RANK DATA= ADCF OUT=W12_RANK;
  WHERE AVISIT=7;
  RANKS CHG_RANK;
  VAR CHG; /*CHG AND BASE ARE BASED ON THE LOG-TRANSFORMED COUGH FREQUENCY*/
RUN;

PROC MIXED DATA=W12_RANK METHOD=REML;
CLASS TRT01PN USUBJID COUNTRY SEX;
MODEL CHG_RANK = TRT01PN COUNTRY SEX BASE / DDFM=KR;
/*CHG AND BASE ARE BASED ON THE LOG-TRANSFORMED COUGH FREQUENCY*/
LSMEANS TRT01PN / CL PDIFF;
  ESTIMATE 'TRT S - P ON DAY 84' TRT01PN -1 1
           / CL LOWER LOWERTAILED;

RUN;
```

A sample of the SAS code for CMH and M&H is provided as below:

SAS PROC FREQ procedure will be used. CRIT1FN is the response variable = '1' (i.e. non-responder as the reference level).

```
PROC SORT DATA=ADAMDATA.ADCF OUT=ADCF;  
BY USUBJID AVISITN;  
WHERE PARAMCD=' XXXXX' AND DTYPE='' AND AVISITN = x;  
RUN;
```

```
/*Treatment comparison using stratified CMH*/  
PROC FREQ DATA=ADCF;  
  TABLES COUNTRY* SEX* TRT01PN* CRIT1FN/CMH  
          alpha=0.1 ;  
  weight Count;  
run;
```

```
/*Estimate difference in proportions (Serlopitant - Placebo) by Country*/  
PROC FREQ DATA=ADCF;  
  TABLES COUNTRY* TRT01PN* CRIT1FN/ riskdiff (cl= MN CORRECT)  
          alpha=0.1 ;  
  weight Count;  
run;
```

```
/*Estimate difference in proportions (Serlopitant - Placebo) by Sex*/  
PROC FREQ DATA=ADCF;  
  TABLES SEX* TRT01PN* CRIT1FN/ riskdiff (cl= MN CORRECT)  
          alpha=0.1 ;  
  weight Count;  
run;
```

```
/*Estimate difference in proportions (Serlopitant - Placebo) by Country and by  
Sex*/  
PROC FREQ DATA=ADCF;  
  TABLES COUNTRY* SEX* TRT01PN* CRIT1FN/ riskdiff (cl= MN CORRECT)  
          alpha=0.1 ;  
  weight Count;  
run;
```

A sample of the SAS code for GLMM analysis is provided as below:

```
PROC SORT DATA=ADAMDATA.ADCF OUT=ADCF;  
BY USUBJID AVISITN;  
WHERE PARAMCD=' XXXXX' AND DTYPE='' AND AVISITN>0;  
RUN;
```

```
PROC GLIMMIX DATA=ADCF;  
CLASS TRT01PN USUBJID AVISITN COUNTRY SEX;  
MODEL CRIT1FN (EVENT='1') = TRT01PN AVISITN TRT01PN*AVISITN COUNTRY  
/ LINK=LOGIT DIST=BINARY ODDSRATIO (DIFF=FIRST);
```

```
RANDOM _RESIDUAL_ / SUBJECT=USUBJID (TRT01PN) TYPE=UN;

/*LS-mean estimates and SEs for proportions Serlopitant vs. placebo*/
LSMEANS TRT01PN*AVISITN / ILINK CL ;

/*Estimates of odds ratio (Serlopitant vs. placebo) and CI at each post-
baseline visit*/
ESTIMATE 'TRT 5mg / P' TRT01PN -1 1,

      'TRT 5mg / P ON DAY 28' TRT01PN -1 1
              TRT01PN*AVISITN -1 0 0 1,
      'TRT 5mg / P ON DAY 56' TRT01PN -1 1
              TRT01PN*AVISITN 0 -1 0 0 1,
      'TRT 5mg / P ON DAY 84' TRT01PN -1 1
              TRT01PN*AVISITN 0 0 -1 0 0 1 / EXP CL UPPER UPPERTAILED;

RUN;
```

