8.3 Derivations of Efficacy Variables

The 24-hour cough frequency (coughs per hour) for a specified visit is calculated as:

24-hour cough frequency = (total number of cough events during the monitoring period (24-hour interval))/24

The awake cough frequency (coughs per hour) is defined as below:

Awake cough frequency = (total number of cough events during the monitoring period (24-hour interval) the subject is awake)/(Total duration (in hours) for the monitoring period the subject is awake)

Awake duration (hours) is time between waking up and sleep during the 24-hour monitoring period.

The cough data will contain all cough events occurring during that 24-hour monitoring period as well as the information about “sleep time” and “awake time”. Any session with duration of recording < 4 hours will be considered as missing.

In general, each 24-hour session is composed by an awake monitoring period and a sleep monitoring period. If a subject did not wake up before the end of the recording session, it will be assumed that the subject slept for the rest of the session. The session will have missing awake time, and the rest of session will be considered under the sleep monitoring period. For any session with both sleep time and awake time missing, the entire 24-hour session will be considered under the awake monitoring period, unless the session has early termination of recording.

On each collection day, the cough count, the actual cough monitoring duration (in hours), and the coughs per hour will be derived for the total 24-hour period, the awake period, and the sleep period, respectively.

The percent change in 24-hour coughs per hour is defined as below:

Percent change in 24-hour cough frequency =

$$\left[\frac{(\text{Change from baseline in 24-hour cough frequency} \times 100)}{(\text{Baseline 24-hour cough frequency})} \right]$$

The proportion of participants with $\geq 30\%$ of reduction from baseline in 24-hour cough frequency is the number of participants with $\leq -30\%$ change in 24-hour cough frequency divided by the total number of participants with available data.

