### 9.6.2.1 Analyses of Primary Endpoint

#### A. Primary Analysis - Mixed Model Repeated Measures Analysis of Log Transformed 24-hour Cough Frequency:

As the change in 24-hour cough frequency may have a skewed and wide distribution, the primary analysis for the primary endpoint will be on the natural log scale of the cough frequency data. The difference between serlopitant 5 mg and placebo will be estimated using a mixed effect repeated measures (MMRM) model. The model will include fixed effects for treatment group, visit, country, sex, the treatment-by-visit interaction, and the log-transformed baseline value as a covariate. The MMRM model will use all available 24-hour cough frequency data on Day 28, 56, and 84. An unstructured covariance structure will be applied for MMRM. In case the model will not converge with the unstructured covariance structure, the heterogeneous compound symmetry (CSH) will be used instead. Furthermore, if the model fails to converge with CSH, the heterogeneous Toeplitz structure (TOEPH) will be used. If the unstructured covariance structure will be used, the denominator degrees of freedom will be computed using the Kenward-Roger method. In case of other covariance structures, the BETWITHIN (SAS®) option will be used for the denominator degrees of freedom. Contrasts will be constructed to compare each of the three serlopitant treatment groups to the placebo group at each visit. The least-squares (LS) mean change from baseline (on the log scale) with the associated standard errors will be displayed for each treatment group. Estimated treatment differences (serlopitant vs. placebo) along with corresponding one-sided 95% CIs and p-values will also be presented at each post-baseline timepoint.

In addition, the geometric mean of 24-hour cough frequency will be presented by treatment and by visit. The percent difference change between serlopitant and placebo will be estimated by  $100(e^{\text{diff}} - 1)$ , where diff is the difference provided by the analysis of the log-transformed variable. A sample of SAS code for MMRM analysis is provided in Appendix A.

An observation of zero coughs per hour will be replaced by a cough rate of 0.1 for the calculation of geometric means.

Missing data, in the assessment of the primary hypothesis, is assumed as missing at random (MAR). This assumption will be assessed with a missing data sensitivity analysis (see Section 9.6.5 Sensitivity analysis of the primary endpoint).

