In addition, the responder endpoint will be analyzed by a generalized linear mixed model (GLMM) with treatment, visit, country, sex, and treatment by visit interaction as fixed effects. Visit ordering will be treated as a repeated measure within subjects. The GLMM model will use all available cough frequency data on Day 28, 56, and 84. The least-squares (LS) mean proportions with the associated standard errors will be displayed for each treatment group. Estimated odds ratio (serlopitant vs. placebo) along with corresponding one-sided 95% CIs and p-values will also be presented at each post-baseline timepoint.

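### The printed code for the primary MMRM names no visit in its REPEATED statement, so a skipped visit can put later values in the wrong covariance position; the GLMM code shares the gap and omits SEX

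*SAP*

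**What the plan says.** SAP 9.6.2.1 A describes the primary model: "An unstructured covariance structure will be applied for MMRM". Its data are whatever was observed: "The MMRM model will use all available 24-hour cough frequency data on Day 28, 56, and 84". If the unstructured fit fails, the fallbacks are CSH and then TOEPH.

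SAP Appendix A gives the code. The visit variable is declared, "CLASS TRT01PN USUBJID AVISITN COUNTRY SEX", and appears in the MODEL statement. The covariance line is "REPEATED / SUBJECT=USUBJID (TRT01PN) TYPE=UN", so no visit is named there. SAP 9.6.3.1 and 9.6.3.3 send awake cough frequency and VAS to the same analysis. The same line recurs in the copy-reference and tipping-point code.

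Visits can be missing with later ones present. Protocol 8.3 (repeated in SAP 8.4) states: "Any session with duration of recording < 4 hours will be considered as missing". SAP 6.1 admits a subject to the FAS with one post-baseline value, and SAP 9.6.5 has an imputation step for intermittent gaps.

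For the responder GLMM, SAP 9.6.3.2 lists "treatment, visit, country, sex, and treatment by visit interaction as fixed effects". The Appendix A code has "MODEL CRIT1FN (EVENT='1') = TRT01PN AVISITN TRT01PN*AVISITN COUNTRY", without SEX, and "RANDOM _RESIDUAL_ / SUBJECT=USUBJID (TRT01PN) TYPE=UN", without a visit.

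**The concern.** With no repeated effect, PROC MIXED fills the unstructured matrix by row order within subject. The documents do not say this; it is how the procedure works. If the rows for missed visits are absent, a subject with Day 56 and Day 84 only has those values treated as positions 1 and 2, and a subject with Day 84 only has it treated as position 1. CSH and TOEPH also have position-specific variances, so the fallbacks do not avoid the problem.

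The program runs without an error message. It produces the p-value that opens the hierarchy of four key secondary tests (SAP 8.7). No text or code in the SAP requires the primary dataset (LOGEFF) to hold a row with a missing response for each skipped visit, or to be sorted by visit.

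The GLMM is also fitted to observed data and has the same gap. Its missing SEX term contradicts its own text whatever the pattern of missing data.

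**Working it through.** **1. The plan's own figure.** SAP 8.2 gives CV 0.64, ratio 0.75, one-sided alpha 0.05, 90% power and 15% dropout.
- Log SD = sqrt(ln(1 + 0.64²)) = 0.5859. Log difference = ln 0.75 = -0.2877.
- Two-sample t-test: 72 per arm, power 0.901.
- 72 / 0.85 = 84.7, so 85 per arm and 170 in total. The stated size reproduces, and this point does not change it.

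**2. Which analyses can have a skipped visit when the model is fitted.**
- Primary, awake frequency and VAS MMRM: yes, because they use observed data.
- Copy-reference and tipping-point MMRM: no. Under SAP 9.6.5, MCMC fills intermittent gaps and the trailing gaps are then imputed. Each FAS subject has at least one post-baseline value, so the first step fills AVAL1 and the second completes AVAL2 and AVAL3. The wide data are then transposed to long, giving three values per subject.
- GLMM: yes, observed data.

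**3. Size, by simulation.** From the SAP: 85 per arm, 15% dropout (taken as monotone), the fixed effects of the primary model, unstructured covariance, Day 84 log SD 0.586. Assumed, because the documents give neither: the share skipping at each of Day 28 and Day 56 (0%, 3%, 10%), and the other SDs and the correlations. Each dataset was fitted twice by REML, once with position equal to the true visit and once with position equal to row order with missing rows absent. Standard errors are normal-theory, without the Kenward-Roger adjustment. There were 40 replicates per setting.

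Ratio of the Day 84 standard error, row order divided by true visit:

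| Log SDs at Days 28/56/84 | Correlations 28-56, 56-84, 28-84 | 0% | 3% | 10% |
|---|---|---|---|---|
| equal (0.586) | 0.7, 0.7, 0.7 | 1.000 | 1.001 | 0.998 |
| equal (0.586) | 0.7, 0.7, 0.49 | 1.000 | 1.000 | 0.993 |
| 0.40/0.50/0.586 | 0.7, 0.7, 0.5 | 1.000 | 0.992 | 0.974 |
| 0.30/0.45/0.586 | 0.8, 0.8, 0.64 | 1.000 | 0.985 | 0.960 |
| 0.80/0.70/0.586 | 0.7, 0.7, 0.5 | 1.000 | 1.006 | 1.010 |

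On average 9.5 of 170 subjects are misplaced at 3%, and 29.2 at 10%. The range is 0.985 - 1 = -1.5% to 1.006 - 1 = +0.6% at 3%, and 0.960 - 1 = -4.0% to 1.010 - 1 = +1.0% at 10%.

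**4. Estimate and type I error under no effect, 10% skipped.** AVISITN stays in MODEL, so the means remain tied to the right visits, and the average estimate was within 0.001 of zero under both fits. Single trials moved by up to 0.139 on the log scale in the strongly growing case. One-sided rejection rates, row order against true visit:
- strongly growing SDs: 0.065 against 0.047 (600 replicates);
- moderately growing SDs: 0.048 against 0.048 (600 replicates);
- equal SDs, correlations all 0.7: 0.050 against 0.040 (300 replicates).

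The Monte Carlo SE at 600 replicates is sqrt(0.05 × 0.95 / 600) = 0.009; at 300 it is 0.013.

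**5. A second simulation.** Settings: 80 per arm, SDs 0.4/0.5/0.6, correlations 0.5 to 0.65, about 15% monotone dropout, 500 trials per scenario. Model SE, row order against true visit: 0.0993 against 0.1008 at 5% gaps (ratio 0.985) and 0.0982 against 0.1009 at 10% (ratio 0.973). The significance call differed in 0.8% to 4.2% of trials.

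**The case against.** The strongest reply is that the SAP calls this sample code, does not show how LOGEFF is built, and loses nothing if ordered blank rows are kept. Setting a short recording to missing does not delete its record. SAP 9.6.3.2 categorises missing responder data, which suggests that missed visits may be represented. Skipped visits may also be few: SAP 8.4 allows repeat monitoring after equipment failure, and the analysis windows in SAP 7.3 are contiguous, so a late recording can still count for its visit. For the GLMM, the text already treats visit order as the repeated measure, and the code sorts by subject and visit.

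Much of this stands, and it makes the point conditional. It does not remove it. Protocol 8.9.2 assigns the implementation code to the SAP, and nothing there requires the blank rows on which the printed code depends. Sorting does not help when a row is absent.

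Three stronger readings are tempting, and the documents do not support them:
- A reader might infer that the sensitivity analyses are also wrong, since they carry the same line. Imputation completes all three visits first.
- A reader might infer that the standard error is always too small. That follows from assuming SDs that grow over visits; with shrinking SDs it is slightly too large.
- A reader might take the filter in the responder code as proof that blank rows are dropped. It tests parameter, derivation type and visit, not whether a response is present.

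**Conclusion.** The point holds as a conditional fault in the printed code for the primary MMRM and for the observed-data models that reuse it. Its expected effect is small to modest, in the range of step 3 above, with a sign that depends on the covariance pattern. Inflated type I error is suggested only in the most adverse setting tried, and Monte Carlo error there is not negligible. All sizes rest on assumed gap rates and covariances. The effect is nil with monotone dropout only, or if an ordered row is kept for every scheduled visit.

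The omission of SEX from the GLMM is a definite mismatch between text and code. It concerns a supportive model, since SAP 9.6.3.2 makes the stratified CMH test the primary responder analysis.

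Both are worth correcting before the code is used: the fault is silent and sits in the test that gates the hierarchy.

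**What to change.** - Primary MMRM, and the awake-frequency and VAS models that reuse it: write `REPEATED AVISITN / SUBJECT=USUBJID(TRT01PN) TYPE=UN;`, and name AVISITN in the same way under the CSH and TOEPH fallbacks.
- The two sensitivity blocks: make the same change, only as a safeguard on row order.
- GLIMMIX: name AVISITN as the residual effect, for example `RANDOM AVISITN / SUBJECT=USUBJID(TRT01PN) TYPE=UN RESIDUAL;`, and add SEX to the MODEL statement.

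The cost is a few words of code. The sample size and the models described in the SAP text do not change, and the MMRM code then matches its text whatever the dataset layout. Requiring a row per scheduled visit, sorted by visit, would also cure the MMRM problem, but it relies on every dataset build following that rule.
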